## INTRODUCTION

Esophageal and stomach cancers, which constitute cancers of the upper region of the digestive system, are cancers that are frequently observed and unfortunately have a low rate of cured patients [1]. Due to the fact that the esophagus and stomach are hollow organs and their capacity to stretch, patients' complaints about nutrition usually occur when the tumor grows and occludes the lumen. Naturally, the tumor is at an advanced stage when diagnosed [2]. The stage of cancer at diagnosis is very important for two reasons; First, the stage of the cancer is directly related to the survival time. Secondly, treatment is planned according to the stage. Different treatments are applied to patients at different stages [3,4].

Currently, the TNM staging (Tumor, Lymph Node and Metastases) system is the accepted one worldwide. According to this system, the depth of the cancer in the tissue (T), spread to lymph nodes and spread to distant organs (M) are evaluated and categorized from stage 1 to stage 4[5]. Despite many advanced technology tools used in staging (Computed Tomography, Magnetic Resonance Imaging, Endoscopic Ultrasonograph), there are still difficulties in correct staging before surgery or before-after neoadjuvant therapy[6]. The Endoscopic Ultrasonograph (EUS) gives the best accuracy (71 - 99%) in "T" staging of esophageal and gastric cancers [6]. However, the number of centers where EUS is located and the number of experienced gastroenterologists who will perform EUS are low. Computed Tomography (CT), Magnetic Resonance Imaging (MRI) are used frequently, but the accuracy rates are reported to be 55-91% [6]. It is certain that the diagnosis and treatment will be better with the increase in the accuracy of cancer staging.

Artificial intelligence techniques are increasingly used in the field of health, especially in the diagnosis and treatment of cancers [7-9]. Obtaining cancer details in radiological images, which cannot be noticed by the human eye, by analyzing big data with the help of algorithms gave rise to the application area of "radiomics" [10]. It is stated that with Radiomiks, there will be improvements in both the diagnosis and staging of cancers and, accordingly, in the treatment.

While there are studies on the use of endoscopic methods with artificial intelligence for the early diagnosis of esophageal cancers, a limited number of studies have been conducted on stage estimation from radiological images [11,13]. In particular, there are not enough studies on the investigation of changes in tumor size after chemotherapy with artificial intelligence and the estimation of staging.

In this study, it was aimed to investigate the predictive efficiency of staging by processing tomography images in a region where esophageal cancers are endemic.

## **METHOD-MATERIAL**

### ***Design***

The study, which included patients with histopathological proven diagnosis of esophageal cancer, was designed prospectively between the years 2021-2022. This research is the first pilot study of an ongoing project of artificial intelligence applications in the staging of upper gastrointestinal tract cancers. The study was carried out in 2 different centers, which are 3rd level training and research hospitals.

Approval was obtained from two separate local ethics committees (Van Training and Research Hospital Ethics Committee 26/12/2019, 2019/22 and Van Yuzuncu Yil University Ethics Committee 15.12.2021, 2021/17).

In both centers participating in the study, all cancer patients are evaluated weekly by the oncology council. Tomography images of esophageal or stomach cancers that come to these councils are recorded. During the council, the "T" stage of the tumor is specified and recorded by the radiologist. According to this pre-treatment clinical staging, which is also confirmed by oncology and general surgery specialists, the treatment protocol that the patients will receive is determined.

In this study, tumors were marked on tomography images of patients who were admitted to the council at the time of new diagnosis or after neoadjuvant therapy (Figure-1). After marking, these images were taught to algorithms developed with the technique described in detail below. Thus, algorithm training is completed with these images.

### ***Duration of study/number of patients***

This study, in which artificial intelligence applications are planned to be developed through tomography images of patients, is planned to last two years. The more data inputs into the study, the better the training of algorithms will be, and the admission of patients will continue throughout the study period. After the last patient is recruited, the final revision of the developed algorithms will be made. The current pilot study was evaluated with data from 50 patients.

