***Primary outcomes:***

The accuracy of the algorithm developed with artificial intelligence to predict the “T” staging in esophageal cancer

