### **Details:**

We will collect all CT images, start from cervical region to upper abdomen. Images from DICOM will be converted to JPEG. Then these images will be classified with help of artificial intelligence (AI) algorithms. Training of algorithm will be performed with data previously collected and testing with new patients when available. New patient images will be evaluated for "T" stage by artificial intelligence algorithms. Then these predictions will be compared with pathological results and parameters below will be measured:

- 1- positive prediction value
- 2- false positive value
- 3- accuracy rate
- 4- sensitivity and specificity

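### The plan assures the final algorithm no untouched study patients: its last revision follows the last recruit, with no version locked and no test patients reserved

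*Combined protocol and SAP*

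**What the plan says.** The single entry under Primary outcomes begins "The accuracy of the algorithm developed with artificial intelligence to predict the" and continues with T staging in esophageal cancer. It names neither a version of the algorithm nor a set of patients.

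The Details section separates training from testing in principle: "Training of algorithm will be performed with data previously collected and testing with new patients when available". For the new patients, the AI's T stage is set against pathology: "Then these predictions will be compared with pathological results and parameters below will be measured". No number of test patients, proportion, cut-off date or reserved centre is given.

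The section Duration of study/number of patients explains why admission stays open, "The more data inputs into the study, the better the training of algorithms will be", and then fixes the order of events: "After the last patient is recruited, the final revision of the developed algorithms will be made". On the pilot it says "The current pilot study was evaluated with data from 50 patients", without assigning those patients to training or testing.

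The Design section says that marked images of study patients were used to teach the algorithms, and adds "Thus, algorithm training is completed with these images". It also describes the work this way: "This research is the first pilot study of an ongoing project of artificial intelligence applications".

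**The concern.** An accuracy figure can be interpreted only if the reader knows which version was scored and whether the scored patients had any part in building it. This plan leaves both open for its sole primary outcome.

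The stated sequence makes this more than a missing detail. If the algorithm is revised after recruitment has ended, any accuracy measured before that belongs to its predecessor. No further study patients are then due, and none were set aside. Two things are at stake. A figure measured on a superseded version could be reported as that of the final algorithm. And for the 50 pilot patients, a reader cannot tell whether the reported accuracy is a test result at all.

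**Working it through.** There is no planned figure to reproduce. The plan does not present the 50 as the result of a calculation, and its sample size formula is given without values for sensitivity, prevalence or alpha. The check is therefore mainly a reading of the sections against each other.

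**Step 1. What each section settles.**

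| Question | Where addressed | Answer given |
|---|---|---|
| Which version supplies the primary accuracy? | Primary outcomes | Not stated |
| When does the algorithm last change? | Duration of study/number of patients | After the last recruit |
| Who is tested? | Details | New patients, when there are any; no number |
| Are any patients withheld from development? | No section | Not stated |
| What was the role of the 50? | Duration of study/number of patients | Not stated |

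**Step 2. What the primary accuracy could then be.** Four courses are compatible with the text:

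1. A version is tested on new patients and revised afterwards. The accuracy is valid for the tested version but not for the revised one.
2. The final revision is made and then tested on patients who arrive later in the wider project. The accuracy is valid for the final version, but the plan does not provide for this step.
3. The 50 were untouched by a version that was not changed afterwards. The accuracy is valid for that version.
4. The revised version is scored on patients used to build it. The accuracy is likely to be too high.

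The plan does not say which course applies, and a reader of the final figure could not find out. In course 1 the figure must not be transferred to the final algorithm; in course 4 it is not a test result.

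**Step 3. What can be computed.** The documents give nothing from which to size the bias in course 4. What can be shown is how much test information the 50 would hold under different roles. The 50 is from the plan. The 70% correct and the subsets of 20 and 10 are assumptions made only for illustration. For x correct out of n, the exact (Clopper-Pearson) 95% limits are

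- lower limit: 2.5% quantile of Beta(x, n − x + 1)
- upper limit: 97.5% quantile of Beta(x + 1, n − x)

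| Untouched patients among the 50 | Correct at 70% | 95% interval |
|---|---|---|
| 50 | 0.70 × 50 = 35 | 55% to 82% |
| 20 | 0.70 × 20 = 14 | 46% to 88% |
| 10 | 0.70 × 10 = 7 | 35% to 93% |
| 0 | none | no test estimate |

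These intervals measure small-sample imprecision and nothing else. The interval for 35/50 is the same whether or not a version is locked.

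**The case against.** The strongest reply is that the Details section already does the right thing: training uses earlier data, testing uses new patients, and the performance measures come from the new patients. A reader might infer from the late revision that training patients will be scored and that the primary accuracy is biased. The documents do not support that. No section says that training patients will be scored, or that the final revision refits on test patients; the content of the revision is not described. Upward bias is a risk that the text leaves open, not a planned step.

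A reader might also infer that no valid test of the final version is possible. That goes too far. The work is described as part of a continuing project, so later patients could serve, and the 50 may already have been untouched. The condition of availability may refer only to timing, and continued admission is also what supplies new patients.

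Nor is there a firm contradiction between the Design section, where training is called complete, and the later revision. The first may concern the pilot and the second the two-year study, or it may simply mean that training was done with these images. A clarifying sentence is enough.

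All of this stands, and it limits the claim. It does not supply what is missing: a principle that depends on patients becoming available assures no test set, and it does not protect a version created after the last recruit. Pilot status excuses a small sample, but not an unidentified primary figure.

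**Conclusion.** The point holds in this form: testing on new patients is sound for the version tested, but as written the final algorithm has no assured untouched study patients. The primary accuracy may therefore describe a superseded version or, if the revised version were scored on patients used to build it, may be biased upward. The conclusion rests on the stated order of events and on the absence, in every section, of a reserved test set, a version lock or a stated role for the 50.

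The size of any bias cannot be derived from the documents. Because the sole primary outcome is affected and readers could not repair the problem afterwards, it should be settled before any accuracy is reported.

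**What to change.** - **Freeze before scoring.** Amend Duration of study/number of patients and Details so that the algorithm version is frozen and named before it is scored. Compute the primary accuracy and the table under Comparing AI success to pathology results for that version, only from patients not used to fit or tune it. Keep all images of a patient on the same side of the split, since a patient may contribute many images and more than one time point.
- **State the role of each of the 50.** If some were untouched, report the test accuracy in those patients only. If all were used for development, make patient-level cross-validation, with tuning inside the training folds, the pilot's primary estimate. Describe it as the performance of the development procedure and not of a named version.
- **Label later revisions.** Describe any revision made after scoring as not independently evaluated unless and until it is tested on later new patients, and do not attach the earlier accuracy to it.
- **Clarify the Design section.** Say in one sentence what training had been completed, and for which version.

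The cost is wording, a version record and perhaps some computation; no new patients are needed. The downsides are real. Scored patients cannot also train the scored version, the reported accuracy may be lower, and the final revision may end the study without a figure of its own. Under cross-validation a binomial interval is only approximate.

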### **Inclusion criteria:**

Each patient meeting the following criteria will be included in the study.

- 1- Being diagnosed with esophageal cancer (adenocarcinoma or squamous cancer) histopathologically
- 2- Being over 18 years old
- 3- Having a tomography image before or after chemotherapy.
- 4- Giving informed consent to participate in the study.
- 5- Having final pathological staging after surgery.

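### The plan does not say which CT is scored or whether treatment may fall between that CT and resection, so one primary accuracy figure may combine staging of the imaged tumour with forecasting of post-treatment stage

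*Combined protocol and SAP*

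**What the plan says.** Under Inclusion criteria, item 3 asks for "Having a tomography image before or after chemotherapy" and item 5 for "Having final pathological staging after surgery". The primary outcome is "The accuracy of the algorithm developed with artificial intelligence to predict the" T stage in esophageal cancer, with no time point attached.

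The Design section reports that "tumors were marked on tomography images of patients who were admitted to the council at the time of new diagnosis or after neoadjuvant therapy", and then "Thus, algorithm training is completed with these images". The Details section collects all CT images and separates the two uses of data: "Training of algorithm will be performed with data previously collected and testing with new patients when available". For the new patients, "Then these predictions will be compared with pathological results and parameters below will be measured".

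Outcome measures lists sensitivity, specificity and accuracy for each of T0 to T4. Comparing AI success to pathology results gives one blank 5x5 table of predicted against pathological T. Neither section mentions scan timing. Measurements parameters lists only the CT images and the pathological T stages, with no dates.

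**The concern.** The target is clear: pathological T in the resected specimen. The input is not, because its place in the treatment sequence is left open. If a patient is scanned, receives neoadjuvant therapy and then has surgery, the specimen shows a treated tumour that the scan did not show. A prediction from that scan is a forecast of response as well as of stage. If no treatment comes between scan and surgery, the same comparison is staging of the tumour as imaged. These are different questions, and a reader would use the answers differently.

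T0 makes the distinction concrete. It is a legitimate pathological result after neoadjuvant therapy. Yet every patient has histologically proven cancer under inclusion criterion 1, so a T0 call on a pre-treatment CT can be right only as a forecast.

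At stake is whether the primary accuracy can be interpreted. If both kinds of scan are scored and accuracy differs between them, the figure could vary from one test set to another with the same algorithm, simply because the share of each kind of scan varies.

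**Working it through.** **Step 1: look for a rule.** The sections where such a rule could sit, set side by side:

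| Section | What it fixes | What it leaves open |
|---|---|---|
| Inclusion criteria, items 3 and 5 | CT from before or after chemotherapy; surgical pathology required | Which CT counts; treatment between CT and surgery |
| Exclusion criteria | Previous thoracic surgery, recurrence, staging not possible, poor image quality | Timing |
| Primary outcomes | Accuracy of predicted T | Time point; stratum |
| Tomography shooting technique | Scanner, acquisition, two readers blind to pathology and AI result | Timing; blinding does not address it |
| Measurements parameters | CT images and pathological T | Scan, treatment and surgery dates |
| Details | All CTs collected; testing on new patients against pathology | Index CT; handling of several CTs |
| Outcome measures and the 5x5 table | Per-stage measures; one table | Separation by timing |

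No section supplies the rule. Item 3 governs every patient, including test patients, so the gap reaches the scored set.

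**Step 2: what pooling could do.** The plan states no accuracy and no split by scan timing, so there is no figure of its own to reproduce. All inputs in this step are assumptions. Let a1 be accuracy on CTs with no treatment between scan and resection, a2 accuracy on CTs taken before neoadjuvant therapy, and f the share of the latter. Then

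pooled accuracy = (1 − f) × a1 + f × a2.

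| a1 | a2 | f = 0.25 | f = 0.50 | f = 0.75 |
|---|---|---|---|---|
| 80% | 60% | 75% | 70% | 65% |
| 80% | 70% | 77.5% | 75% | 72.5% |
| 80% | 80% | 80% | 80% | 80% |
| 60% | 80% | 65% | 70% | 75% |

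For example, 0.5 × 80% + 0.5 × 60% = 70%. The last row reverses the direction, because nothing in the documents says which kind of scan is easier to predict from. With f = 0 or a1 = a2 the mix has no effect. For scale, the section with the 5x5 table names 5% as the precision that matters; in the first two rows the shift from 80% runs from 2.5 to 15 points.

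**Step 3: what splitting costs in precision.** Wilson 95% interval, z = 1.96:

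[p + z²/(2n) ± z × √(p(1 − p)/n + z²/(4n²))] / (1 + z²/n).

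The section on duration and number of patients says the pilot was evaluated with 50. Assume that all 50 are test cases and that accuracy is 80%:

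- 40/50 correct: 67.0% to 88.8%.
- 20/25 correct (half the patients in one stratum): 60.9% to 91.1%.

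For per-stage sensitivity, assume the 25 are spread evenly over five stages, which leaves 25/5 = 5 per stage. Then 4/5 correct gives about 38% to 96%.

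**The case against.** The strongest reply is that the target is consistent throughout. Predicting surgical pathological T from whatever CT the council has is a coherent pragmatic aim, and the Introduction names change after chemotherapy as an under-studied question. On this view, what is missing is specification and reporting, and no bias has been demonstrated. That much stands, and it is why the point concerns what the plan permits. It does not remove the gap: an intended forecast should still be labelled as one and kept distinguishable from staging.

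A reader might infer from the Design section that mixing did occur, since scans from diagnosis and from after neoadjuvant therapy were both marked. The documents do not support this for the scored set: those are described as training images, and Details tests on new patients.

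A reader might also infer that test sets with different scan timing would necessarily give different accuracies, or that pooling lowers the result. Neither follows. Accuracy may be equal in the two kinds of scan, and the documents give no ground for a direction. The training label is also not stated; an algorithm trained on pathological T could learn to forecast.

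Finally, simply restricting the primary table to scans with no treatment before resection is not a clean remedy. It would still mix patients who went straight to surgery with patients scanned after neoadjuvant therapy, and it would drop eligible patients whose only CT preceded chemotherapy. This objection is sound, and the fix is built to avoid both effects.

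**Conclusion.** The concern holds as a missing rule with a consequence for the primary outcome. The eligibility text admits scans on either side of chemotherapy against one surgical reference. Nothing names the scored CT, limits treatment between scan and resection, or separates the results. Confidence is high on that omission. On its effect there is no evidence either way: the documents do not show that mixing occurred, how large it is, or in which direction it acts. The illustrative shifts of 2.5 to 15 points from 80% rest wholly on assumed accuracies and shares, and vanish if the accuracies are equal or only one kind of scan is scored. This should be fixed before the test set is scored.

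**What to change.** - Name one index CT per patient in advance for the primary 5x5 table: the last CT before surgery.
- Record scan, neoadjuvant treatment and surgery dates for each scored image.
- Report the same table by timing stratum, with the count in each: (a) surgery without neoadjuvant therapy; (b) CT after neoadjuvant therapy, with no further treatment before resection; (c) CT before neoadjuvant therapy that was followed by surgery.
- Label (c) as prediction of post-treatment pathological T, and do not present it as staging accuracy. A patient whose only CT preceded chemotherapy stays in the analysis, in (c).
- Where a patient has both scans, report the earlier one only in (c), as a secondary analysis.
- Keep pathology as the reference throughout. State the training label (pathological T or council T) and the timing of the training images.

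The cost is protocol and SAP wording, three dates that Measurements parameters does not now list, and the stratified tables. Whether retraining is needed cannot be judged until the training label and image timing are stated. The main downside is precision: with strata of about 25 or fewer, overall accuracy is loosely estimated and per-stage sensitivity far more so, as the intervals above show. Stratum results should therefore be presented as descriptive in this pilot.

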### **Exclusion criteria:**

A participant with any of the following criteria will be excluded from the study:

- 1- Previous thoracic surgery.
- 2- Having a recurrent tumor
- 3- Inability to perform clinical staging due to technical reasons
- 4- Drawings cannot be made due to poor tomography quality.

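### Exclusion items 3 and 4 limit the primary accuracy to scans that could be staged and drawn; the patients removed should stay in the test set and be counted

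*Combined protocol and SAP*

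**What the plan says.** The Exclusion criteria open with a rule that covers the whole study, not only algorithm training: "A participant with any of the following criteria will be excluded from the study". Items 1 and 2 (earlier thoracic surgery, recurrent tumor) describe the patient. Item 3 is "Inability to perform clinical staging due to technical reasons". Item 4 is "Drawings cannot be made due to poor tomography quality".

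The Inclusion criteria already require a scan, "Having a tomography image before or after chemotherapy" (item 3), and a reference standard, "Having final pathological staging after surgery" (item 5).

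The primary outcome is "The accuracy of the algorithm developed with artificial intelligence to predict the “T” staging in esophageal cancer". The Details section describes how new patients' AI stages are scored: "Then these predictions will be compared with pathological results and parameters below will be measured". The section on comparing AI success to pathology lays out a table of AI T0 to T4 against pathology T0 to T4. Accuracy there is the sum of the diagonal divided by the sum of the 25 cells, A to Y. The table has no row for a patient without an AI stage. Nothing in the document provides for counting, describing or separately analysing patients removed under items 3 or 4.

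**The concern.** Items 3 and 4 differ in kind from items 1 and 2. They become known only when someone has tried to stage the scan or outline the tumor, so they select patients by how readable the image is. A patient removed this way can still have both quantities listed under Measurements parameters, the CT images and the pathological T stage.

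Item 3 is the harder one to justify. The clinical T stage is the radiologist's assessment at the oncology council (Design section). It is not a cell, margin or input of the AI-versus-pathology table, so its absence does not prevent a prediction from being scored.

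What is at stake is the population to which the headline figure applies. If less readable scans are also harder for the AI, the reported accuracy will be better than the accuracy met in all eligible patients. Without a count of those removed, a reader cannot judge whether this matters.

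**Working it through.** **No figure of the plan to reproduce.** The document gives no accuracy, no number removed under items 3 or 4, and no expected share. The only count is the 50 patients of the pilot (Duration of study/number of patients). The point is therefore structural, and its size can only be bracketed.

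**Step 1: which steps the scoring needs.**

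| Element | Needed to score an AI stage? | Source |
|---|---|---|
| CT images | Yes | Inclusion item 3; Measurements parameters |
| Pathological T stage | Yes | Inclusion item 5; Measurements parameters |
| Clinical T stage (exclusion item 3) | No | Details; comparison table |
| Drawn tumor (exclusion item 4) | Not stated for test scans | Design ties marking to training; Details does not mention drawing of new images |

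**Step 2: effect on the denominator.** Let p be the accuracy among patients kept, u the share of otherwise eligible patients removed by items 3 and 4, and a the proportion of the removed whom the AI would stage correctly. Accuracy over all eligible patients is then

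p × (1 − u) + a × u,

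and the reported figure exceeds it by u × (p − a). The difference is positive if a < p, zero if a = p and negative if a > p. The document gives none of p, u or a.

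**Step 3: range for assumed values.** The lower limit sets a = 0 and the upper limit sets a = 1.

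| Assumed p | Assumed u | a = 0 | a = 1 |
|---|---|---|---|
| 80% | 5% | 0.80 × 0.95 = 76% | 76% + 5% = 81% |
| 80% | 10% | 0.80 × 0.90 = 72% | 72% + 10% = 82% |
| 80% | 20% | 0.80 × 0.80 = 64% | 64% + 20% = 84% |

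**Step 4: in patient numbers.** Suppose that all 50 pilot patients are scored (the document does not say how many are test patients), that 45 are correct, and that 3 more had been removed.

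- Reported: 45/50 = 90.0%.
- None of the 3 correct: 45/53 = 84.9%, a fall of 5.1 points.
- All 3 correct: 48/53 = 90.6%, a rise of 0.6 points.

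The comparison section names 5% as the precision that matters. On these assumptions, three removals could in the worst case move the figure by about that amount.

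**The case against.** A reader might infer that the removed patients are failures of the AI and that the primary accuracy is therefore inflated. The documents do not support that.

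- **Not AI failures.** Item 3 is a failure of clinical staging and item 4 a failure of the radiologists' drawing. The test being scored is the algorithm.
- **Drawing of test scans is left open.** The Design section links marking to training, and the Details section has new images staged by the AI without mentioning drawing. If drawing serves training only, an undrawable scan can still receive an AI stage, and scoring it automatically as wrong would be a mistake. The same applies to item 3 patients, because the clinical stage is not used in the scoring.
- **Direction not established.** The illustrative limits fall on both sides of the assumed accuracy.
- **A CT image need not be a usable one.** The Inclusion criteria ask for a scan but set no quality standard. The technical reasons in item 3 are undefined and may lie in the imaging itself.
- **Blinding.** The tomography section says the readers did not know the pathology or the AI result. If they judged whether a scan could be drawn, removal was not chosen on whether the AI was right.
- **A legitimate pilot quantity.** Accuracy among interpretable images is a reasonable measure of technical performance in a first pilot, and an undrawable scan cannot serve as a marked training image.

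All of this stands, and it rules out a claim of demonstrated inflation. It does not close the gap: exclusion is study-wide, so it reaches the test set as well as training, and the plan provides no count of those removed. Blinding does not prevent selection by image quality.

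**Conclusion.** The point holds as a limit on what the primary accuracy describes. Followed as written, the plan estimates accuracy among patients whose scans could be clinically staged and drawn, and that figure may not hold for all eligible patients. The reported value could be too high, too low or about right, depending on how the AI performs on the removed scans.

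The size is unknown. With an assumed accuracy of 80% and 10% removed, the figure for all eligible patients lies between 72% and 82%. This bracket rests on both assumed values and on the removed patients having a CT and a pathological stage. The Inclusion criteria imply that they do, but do not guarantee a readable scan. The case for a change rests on its low cost and on the missing count, not on a proven bias.

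**What to change.** 1. Keep item 4 as a reason to leave a scan out of training only. Apply neither item 3 nor item 4 to the test set.
2. State whether a test scan must be drawn before the AI can stage it, and define the technical reasons in item 3.
3. Run the AI on these patients' scans wherever it can produce a prediction, and score that prediction against pathology like any other.
4. Add a 'no AI stage' row to the comparison table, used only for scans where no prediction results.
5. Report the number of patients affected by each item. Give accuracy among patients with an AI stage and, beside it, the proportion correctly staged among all test patients with CT and pathology, with 'no AI stage' counted as not correct.

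The cost is a change to how eligibility applies to the test set, one table row, one more proportion and slightly more analysis, with no new procedure for patients. The second figure may be lower than the first. For pilot patients already removed, the scans or pathology may not have been kept; the number and reason for each removal should then still be reported if they can be recovered.
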